Our research team developed the first mHealth app for smoking cessation based on ACT—called SmartQuit—in 2013 (PI: [name], Fred Hutchinson Cancer Research Center Hartwell Innovation Fund). We then conducted the first RCT comparing two smartphone apps for smoking cessation—SmartQuit vs. NCI’s QuitGuide. Based on previously successful methods for national recruitment in our trial of web-based ACT [62], we recruited via Facebook ads, Google ads, and a press release developed by the FHCRC communications department. These efforts yielded 738 participants screened, 400 eligible, 340 consented, and 196 randomized (98 per arm). The recruitment sources were: 39% from Facebook ads, 38% from press-release generated media, and 23% from other sources. To maximize outcome data survey completion, we followed a protocol that sequentially timed the administration of separate survey modalities until the survey was completed: first via the web, then by telephone, and then by mail. Participants were compensated \$25 for completing the survey. The achieved outcome survey completion rate of 84%, much higher than the 54% typically obtained in web-based cessation trials [63-68], provided confidence in the effectiveness of our follow-up survey methods for maximizing data retention. Retention did not differ between arms. SmartQuit participants had higher engagement with their assigned app ($p < .0001$) and a descriptively higher quit rate than the QuitGuide app at 2 months post-randomization: 13% (95% CI: 6%-22%) in SmartQuit vs. 8% (95% CI: 3%-16%) in QuitGuide.

We developed the second version of the app (SmartQuit 2.0) in 2014 (PI: [name], Washington State Life Sciences Development Fund). Using data from the trial of SmartQuit 1.0, we evaluated which features of the app were most used and how feature usage was associated with quitting. Based on that analysis [69], the app was restructured to funnel users to the features that showed the strongest relationships with quitting. This method yielded an 8-exercise program with a core feature that prompted users to track when they let an urge pass—a major focus of the ACT exercises and a strong correlate of quitting in the SmartQuit 1.0 trial [69]. Relative to SmartQuit 1.0, we found that SmartQuit 2.0 had better user satisfaction (84% vs. 59%), although the estimated quit rate was similar (11% vs. 13% achieved 30-day PPA at 2 months).

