4.0 OVERVIEW OF CLINICAL TRIAL

4.1 Study Objectives

- 4.1.1 **Primary Objectives:** Assess and compare treatment acceptability across treatment arms.
- 4.1.2 **Secondary Objectives:** Preliminarily assess efficacy and mechanism of change for the behavioral activation app (Actify) vs. the USCPG app (QuitGuide) for smoking cessation.
- 4.1.3 **Tertiary Objectives:** Determine whether there is evidence of differential efficacy in smokers with vs. without pre-quit depressive symptoms

4.2 Study Population:

We will recruit 240 adult smokers, both with (PHQ=8 score 5-19; n=120) and without (PHQ-8 score 0-4; n=120) depressive symptoms, who are interested in quitting smoking. Participants will be recruited nationally via recruitment strategies used successfully in our previous studies: targeted Facebook ads, Craigslist ads in states with a high prevalence of smoking or racial/ethnic minority residence (to achieve the target 25% racial/ethnic minority representation in the sample), other free methods of advertising on the Internet (e.g., Reddit, Twitter), ResearchMatch.org, and earned media generated by press releases from the Fred Hutch media team.

Inclusion of Women & Minorities.

Our previous trials suggest that, without intervention to diversify the sample, the vast majority of participants would be Caucasian and female. To attain adequate representation of racial/ethnic minorities and men, we will cap enrollment of Caucasians and women at 75% of the sample via our online screening and enrollment process for the pilot trial. We anticipate that these caps will be necessary and that the resulting sample will be 25% male and 25% racial/ethnic minority. If needed, we will use targeted Facebook and Twitter campaigns specifically to recruit men and/or people with racial/ethnic minority affiliations (the ad platform's proxy for race/ethnicity). Based on demographic data from our recent trial of a technology-delivered cessation intervention using similar recruitment procedures [8], we expect the following percentages of racial minority participants: African American (10%), Native American or Alaska Native (2%), Native Hawaiian or Pacific Islander, Asian (2%), or other/multiple races (5%). In terms of ethnicity, we expect 8% to identify as Hispanic or Latino.

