Additional exploratory analyses will be conducted. To explore differential treatment effects by pre-quit depression, we will preliminarily test the interaction of treatment group assignment and pre-quit depression and present descriptive data on quit rates for the four subgroups (Actify, depressed; Actify non-depressed; QuitGuide, depressed; QuitGuide non-depressed). To evaluate the theory underlying BAT-D for smoking cessation, we will examine change in BADS scores between baseline and 8-week follow-up as a predictor of 30-day PPA at 6-month follow-up using a logistic regression model. To generate empirical evidence to set usage benchmarks for the Actify app, we will evaluate the relationship between app “dosage” and cessation outcomes by regressing 30-day PPA at 8 weeks on objective measures of app utilization (e.g., number of app logins, total duration of use) using logistic regression. Similar to our feature analysis of SmartQuit that guided future app development [69], we will also regress 30-day PPA at 8 weeks on utilization of specific app components (e.g., scheduling, mood tracking) to determine “active ingredients.” To evaluate the relationship between user characteristics and treatment utilization and outcomes, we will use logistic (for cessation outcomes) or negative binomial (for login count data) models and baseline data as predictors. To examine sex as a biological variable, we will preliminarily test for sex differences in treatment response by descriptively examining results separately by sex.

Missing data: Consistent with prevailing standards for smoking cessation trials [88], participants with missing smoking data will be considered non-abstinent in the primary analysis. As a sensitivity analysis, we will also report abstinence rates from complete case analyses and multiple imputation. Treatment acceptability and mechanism of change (i.e., behavioral activation [BADS] and depression [PHQ-8] scores) will be analyzed using complete case analysis.

Modified intent-to-treat approach. Because treatment acceptability is the primary outcome of this pilot trial, and because a valid assessment of acceptability is not possible in cases where there is pre-intervention attrition (i.e., never downloading or opening the assigned app), we will use a modified intent-to-treat approach in which only those participants who open their assigned app at least once will be included in the outcome analyses.

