14.3 Sample Size and Power

As a pilot treatment development project, this study is not powered to detect statistically significant differences by treatment group. However, we plan to compare the outcomes of the two interventions to obtain a preliminary estimate of effect size. We will use these pilot data to optimize the treatment and study design and to prepare for a rigorous test of the efficacy of Actify in a subsequent R01. We plan to accrue a total of 240 patients in the pilot RCT for a balanced design. The NIDA Stage Model of behavioral treatment development suggests that pilot treatment development trials should include approximately 15-30 participants per arm to test feasibility [61]. However, as demonstrated in a recent simulation focused on sample size for pilot studies [87], binary outcomes (e.g., smoking abstinence) require higher sample sizes for reasonable precision of the effect size estimate than do continuous outcomes. To be conservative, and in consideration of the higher recruitment capacity in remotely conducted studies involving standalone mHealth interventions, we chose to include 60 subjects per arm within each stratum (depressed vs. non-depressed), as a sample size of 60 is a point of diminishing returns in terms of precision of effect size estimates for binary outcomes [87]. Thus, each arm will have 120 participants, of which 60 will meet criteria for mild to moderate depression.

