14.4 Randomization

Following completion of the baseline survey, the web-based program will randomize participants to receive either Actify or QuitGuide with a 1:1 allocation ratio. The randomization algorithm will be developed by the study biostatistician, with stratification by presence of mild to moderate depressive symptoms (PHQ-8 < 5 or PHQ-8 ≥ 5), sex assigned at birth (2 levels: male or female) and level of smoking (2 levels: 20 or more cigarettes per day vs. < 20). Randomized participants will be emailed a secured link to download their assigned app. All participants will be emailed identical once-weekly reminders to use their assigned intervention. Although we project, based on recent data from our trial of web-based interventions [8], that the vast majority (92%) of outcome assessments will be completed via web-based survey, any outcome evaluator who has direct contact with participants will be blinded to treatment group assignment.

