Additional exploratory analyses will be conducted. To explore differential treatment effects by pre-quit depression, we will preliminarily test the interaction of treatment group assignment and pre-quit depression and present descriptive data on quit rates for the four subgroups (Actify, depressed; Actify non-depressed; QuitGuide, depressed; QuitGuide non-depressed). To evaluate the theory underlying BAT-D for smoking cessation, we will examine change in BADS scores between baseline and 8-week follow-up as a predictor of 30-day PPA at 6-month follow-up using a logistic regression model. To generate empirical evidence to set usage benchmarks for the Actify app, we will evaluate the relationship between app “dosage” and cessation outcomes by regressing 30-day PPA at 8 weeks on objective measures of app utilization (e.g., number of app logins, total duration of use) using logistic regression. Similar to our feature analysis of SmartQuit that guided future app development [69], we will also regress 30-day PPA at 8 weeks on utilization of specific app components (e.g., scheduling, mood tracking) to determine “active ingredients.” To evaluate the relationship between user characteristics and treatment utilization and cessation outcomes, we will use logistic (for cessation outcomes) or negative binomial (for login count data) models and baseline data as predictors. To examine sex as a biological variable, we will preliminarily test for sex differences in treatment response by descriptively examining results separately by sex.

Missing data: Consistent with prevailing standards for smoking cessation trials [88], participants with missing smoking data will be considered non-abstinent in the primary analysis. As a sensitivity analysis, we will also report abstinence rates from complete case analyses and multiple imputation. Treatment acceptability and mechanism of change (i.e., behavioral activation [BADS] and depression [PHQ-8] scores) will be analyzed using complete case analysis.

8 DSM plan administration

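### The plan says it will test sex differences in treatment response, but looking at each sex separately neither tests nor estimates the difference; an arm-by-sex estimate with its 95% CI is needed

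*Combined protocol and SAP*

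**What the plan says.** Among the additional exploratory analyses, section 14.2 states that for sex as a biological variable "we will preliminarily test for sex differences in treatment response by descriptively examining results separately by sex". DSMP section 7.2 repeats the sentence. Neither place names an arm-by-sex term, a contrast between the sexes, or a confidence interval for one.

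Earlier in the same paragraph, pre-quit depression is handled differently: "we will preliminarily test the interaction of treatment group assignment and pre-quit depression", with quit rates for the four subgroups shown as description.

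Sex enters the design in two other places. It is a two-level randomization stratum (section 14.4), and section 14.2 names it among the adjustment factors for the linear models. The user-characteristics models take baseline data as predictors, but no interaction with arm is stated.

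On numbers, section 14.3 says "Thus, each arm will have 120 participants, of which 60 will meet criteria for mild to moderate depression". Section 4.2 expects that "the resulting sample will be 25% male and 25% racial/ethnic minority". Section 14.3 also says that the pilot is not powered for differences between arms.

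**The concern.** The sentence promises a test and then describes a procedure that cannot supply one. Whether the effect of Actify over QuitGuide differs by sex is a question about one quantity: the effect in men minus the effect in women. Two separate displays do not give that quantity or its uncertainty. A reader has to compare them by eye, and with few quitters per cell a visible gap, or even a reversal, is an ordinary result when the true effects are equal.

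Section 14.3 says the pilot is meant to give a preliminary effect-size estimate and to prepare a larger efficacy trial. For effect modification by sex, that estimate is the interaction with its interval, which the plan leaves out. Without it, an apparent sex difference could be taken too seriously, and an apparent similarity could be read as evidence of no difference.

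**Working it through.** **Plan's own figure.** 60 per arm per depression stratum × 2 strata × 2 arms = 240, or 120 per arm. This reproduces. No power, precision or effect size is stated for sex.

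**Inputs**
- Men per arm: 120 × 0.25 = 30. Women per arm: 120 × 0.75 = 90. Allocation is 1:1 and stratified by sex (section 14.4), so equal arms within sex are assumed.
- Quit rates: the plan gives none. Section 2.2.3 reports "13% (95% CI: 6%-22%) in SmartQuit vs. 8% (95% CI: 3%-16%) in QuitGuide" at 2 months; 13% vs 8% is taken as an assumption, the same in both sexes.
- Missing smoking status counts as non-abstinent (section 14.2), so the full n is used. Excluding people who never open the app could lower it.

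**How often the sexes point in opposite directions.** Within each sex, quitters are Binomial(n, 0.13) on Actify and Binomial(n, 0.08) on QuitGuide. Exact enumeration of the sign of the difference gives:
- Men (n = 30; expected quitters 3.9 vs 2.4): favours Actify 0.664, tie 0.140, favours QuitGuide 0.196.
- Women (n = 90): favours Actify 0.837, tie 0.054, favours QuitGuide 0.110.
- Strictly opposite: 0.664 × 0.110 + 0.196 × 0.837 = 0.237.

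The table varies the rates and compares the expected split with equal numbers of each sex (60 and 60 per arm).

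| True rates, both sexes | Opposite, 30 men / 90 women | Opposite, 60 / 60 |
|---|---|---|
| 8% vs 8% | 35.9% | 37.4% |
| 13% vs 8% | 23.7% | 22.6% |
| 16% vs 8% | 14.1% | 11.5% |
| 20% vs 10% | 11.3% | 8.4% |
| 19% vs 8% | 7.7% | 4.9% |
| 19% vs 6% | 3.8% | 1.7% |

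With 27 men and 81 women per arm (some participants not analysed), 13% vs 8% gives 24.3%.

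**Precision of the sex contrast at 13% vs 8%**
- Variance term: 0.13 × 0.87 + 0.08 × 0.92 = 0.1867.
- SE in men: √(0.1867/30) = 7.89 points. SE in women: √(0.1867/90) = 4.55 points.
- 95% half-widths: 1.96 × 7.89 = 15.5 and 1.96 × 4.55 = 8.9 points.
- SE of the difference: √(7.89² + 4.55²) = 9.11. Half-width: 1.96 × 9.11 = 17.9 points.
- Detectable with 80% power at two-sided 5%: 2.80 × 9.11 = 25.5 points.
- Odds scale: the SE of the log ratio of odds ratios is √(0.748 + 0.249) = 0.998. The CI is the estimate divided and multiplied by exp(1.96 × 0.998) = 7.1. With 60 per arm in each depression stratum, the same calculation gives a factor of 5.4.

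**Continuous outcomes (normal approximation, SD units).** The interaction SE is √(2/30 + 2/90) = 0.298, half-width 0.58 SD. Opposite directions occur in 50%, 27%, 14% and 6% of trials at true effects of 0, 0.2, 0.3 and 0.4 SD.

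**The case against.** The strongest reply is that the sentence is hedged and the plan has a hierarchy. The analysis is labelled exploratory, preliminary and descriptive, in a pilot that disclaims power. Depression moderation is a tertiary objective (4.1.3) and an exploratory endpoint (4.3.3), and the sample is built on depression strata; sex differences appear in neither list. Giving depression a formal interaction and sex less attention is therefore defensible. A sex interaction would also be too imprecise to decide anything.

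Much of this stands. It keeps the point minor, and the different ranking of the two moderators is not in itself an error. It does not turn a side-by-side display into a test. Imprecision argues for printing the interval, because the interval is what shows a reader how little is known. The planned depression interaction is not much tighter (a factor of 5.4 against 7.1).

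Three stronger readings are tempting and should not be drawn.
- A reader might blame the 25% share of men. The men's estimate is noisier, but an even split moves the 13% vs 8% figure only from 23.7% to 22.6%.
- A reader might use the normal approximation and quote 33%. With about 4 and 2 expected quitters among men, ties are common, and the exact figure of 24% is the right one.
- A reader might expect the plan to set significance in women against non-significance in men. No within-sex significance tests are planned. At 13% vs 8% they would have only about 20% power in women (5/4.55 = 1.10 SEs) and 10% in men (5/7.89 = 0.63 SEs).

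**Conclusion.** The concern holds as a minor defect. The stated method cannot answer the question it is given, in both places where it appears, and no estimate of the sex difference with its uncertainty is planned anywhere.

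The risk of misreading is real but depends on the true effect: about 24% of trials at 13% vs 8%, and about 4% to 36% over the rates checked. It is driven mainly by small numbers and low quit rates. These figures assume equal true effects in both sexes, the full planned sample, 25% men, and rates borrowed from a trial of a different app. The text-based part of the finding needs none of these assumptions.

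The documents do not say that by-sex results will determine the design of the later trial, so harm there is possible but not shown.

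**What to change.** In section 14.2 and DSMP section 7.2, replace the sentence on sex with wording such as: *Effect modification by sex will be estimated with an arm-by-sex term added to the main model for satisfaction, log-ins and 30-day PPA at 8 weeks. The estimate and its 95% confidence interval will be reported as exploratory and imprecise, with no significance claim. Results within each sex will be shown beside it as description.*

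Two details should be settled at the same time. First, name sex as a main effect in the logistic model, since that sentence refers only to a single stratification variable. Second, state the scale for abstinence. At an 8% quit rate, 30 QuitGuide men would include no quitters with probability 0.92^30 = 8%, and the odds-ratio interaction would then not be estimable. The difference in risk differences (about ±18 points) remains available as a point estimate, although its interval would need a small-sample method in that case.

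The cost is one model term per outcome and a few sentences, with no new data. The downside is three more exploratory estimates with wide intervals.

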7.5 Participant Compensation

Participants will receive up to \$124 for participating in this study. Specifically, at 2- and 6-month follow-ups, participants will receive compensation based on the following structure:

- \$2 in a pre-incentive letter for each follow-up (for a total of \$4)
- \$25 for each follow-up survey completed in any modality (for a total of up to \$50)
- \$10 bonus for completing the follow-survey within 24 hours of the initial email invitation (for a total of up to \$20)
- \$25 for completing saliva cotinine and smartphone application-based carbon monoxide testing, if asked, after the 2-month and the 6-month follow-up study survey (for a total of up to \$50)

Participants whose data are flagged for potential deception related to study eligibility criteria (e.g., age, US residence) will be contacted prior to compensation being provided in order to confirm eligibility. If eligibility cannot be confirmed, participants will not be compensated.

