Efficacy for smoking cessation will be self-reported 30-day point prevalence abstinence (PPA) at 8 weeks post-randomization (“Have you smoked at all, even a puff, in the last 30 days?”), consistent with our previous RCT of SmartQuit vs. QuitGuide for smoking cessation [10]. Secondary efficacy endpoints include: (1) 30-day PPA at 6-months post-randomization, (2) 7-day PPA at 8 weeks and 6 months, and (3) no use of cigarettes and other non-medicinal nicotine/tobacco products at 8 weeks and 6 months, including e-cigarettes. Use of these products will be measured at baseline and at 8-week and 6-month follow-up. Generally, biochemical verification of smoking abstinence is considered unnecessary in population-level interventions with no face-to-face contact [77]. However, we will confirm self-reported abstinence among those who report 30-day PPA at 8 weeks and at 6 months using saliva cotinine and expired carbon monoxide. Based on the just-published expert recommendations on biochemical confirmation of tobacco use and abstinence [90], our biochemical verification procedures will include both saliva cotinine testing as well as remote carbon monoxide (CO) monitoring using iCO Smokerlyzers. Both the cotinine tests and the Smokerlyzers will be sent to participants by mail. Participants will complete the CO testing on their smartphones using the iCO app and send results to the study team via email, using a function available within the app. We will also ask them to take a photo of the cotinine test results and return it via email. Aside from analysis of minor tobacco alkaloids (anabasine/anatabine, which require a urine sample and laboratory testing that would not be feasible in a remotely-conducted trial), this combination of methods is the best available approach that is feasible in a trial of this nature for differentiating distinct forms of nicotine and tobacco use. In order to meet the definition of biochemically-confirmed smoking abstinence, only the CO testing must be negative (<6 ppm for CO[1]). For analysis of abstinence from all forms of nicotine and tobacco, the CO test must be negative and the saliva cotinine must be negative for all abstainers who do not report recent (past 72 hours) use of nicotine replacement therapies. For those who report recent use of NRT, there is no feasible method of differentiating therapeutic use of nicotine from other forms of nicotine intake in this trial. We will report both self-reported abstinence and biochemically confirmed abstinence in all reports of study outcomes.

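### Complete-case analysis of biochemically confirmed abstinence is biased low, because among survey responders only self-reported abstainers can lack a test result

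*Combined protocol and SAP*

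**What the plan says.** Section 14.2 (Missing data) gives one rule for all abstinence outcomes: "participants with missing smoking data will be considered non-abstinent in the primary analysis". As sensitivity analyses, "we will also report abstinence rates from complete case analyses and multiple imputation". The monitoring plan (Appendix A, Section 7.2) repeats both statements.

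Section 8.3 sets out the confirmation step: "we will confirm self-reported abstinence among those who report 30-day PPA at 8 weeks and at 6 months using saliva cotinine and expired carbon monoxide". Testing is remote: "Both the cotinine tests and the Smokerlyzers will be sent to participants by mail". Participants run the CO reading on their own phone and email back the result and a photo of the cotinine test. For confirmed smoking abstinence, "only the CO testing must be negative". Section 7.5 pays $25 at each follow-up "for completing saliva cotinine and smartphone application-based carbon monoxide testing, if asked".

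Confirmed abstinence is a secondary endpoint. The leading cessation endpoint is self-reported 30-day abstinence at 8 weeks (Protocol Synopsis; Appendix A, Section 1.2). Section 8.3 adds: "We will report both self-reported abstinence and biochemically confirmed abstinence in all reports of study outcomes".

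Four things are not stated: how a self-reported abstainer without a test result is classed, what a complete case is for a confirmed endpoint, whether the imputation model covers the test result, and what share of kits is expected back. The 89% retention in Section 7.4 refers to surveys.

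**The concern.** A self-reported smoker has a known confirmed outcome without giving any sample. A self-reported abstainer has one only if the kit comes back. Among people who answer the survey, a missing confirmed outcome is therefore confined to those who may be abstinent. Two things follow.

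- In the main analysis the confirmed rate mixes kit return with abstinence, and no planned table separates an unreturned kit from a failed test.
- The complete-case analysis, which a reader would take as the check on the conservative rule, leaves out abstainers and keeps smokers. It errs in the same direction as the rule it is meant to test.

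Section 2.1.2.a lists missing biochemical verification among the limitations of earlier app studies that this trial will address, and Section 14.3 says that the pilot should supply a preliminary effect size for a larger trial. A confirmed rate that partly measures kit return is a poor planning input for that trial.

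**Working it through.** **The plan's own figure.** Section 14.3: 60 per arm per stratum × 2 strata × 2 arms = 240, so 120 per arm. This reproduces. No kit-return rate, pass rate or confirmed quit rate is given, so there is nothing further to reproduce.

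**Inputs**
- n = 120 per arm (Section 14.3).
- Survey response 89% (Section 7.4): 120 × 0.89 = 106.8 responders and 13.2 non-responders per arm.
- Self-reported abstinence p = 13% of those randomised. This is an assumption, taken from the higher arm of the earlier app trial (Section 2.2.3: 13% vs 8%).
- Kit return r: assumption, 50% to 100%.
- Pass rate among returned tests c: assumption, 90% in steps 1 and 2, and 100% in step 4.
- All self-reported abstainers are survey responders: A = 120 × 0.13 = 15.6, leaving 106.8 − 15.6 = 91.2 self-reported smokers.

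The working is for 30-day abstinence. Confirmed 7-day abstinence has a further gap: it is an endpoint, but only 30-day reporters are tested.

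**Step 1. Main analysis.** Rate = p × r × c.
- r = 50%: 0.13 × 0.5 × 0.9 = 5.85%
- r = 80%: 0.13 × 0.8 × 0.9 = 9.36%
- r = 100%: 0.13 × 0.9 = 11.7%

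**Step 2. Complete case, with return random among abstainers.** Rate = A·r·c / (91.2 + A·r).
- r = 50%: 7.02 / 99.0 = 7.1%
- r = 80%: 11.23 / 103.68 = 10.8%
- r = 100%: 14.04 / 106.8 = 13.1%

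Suppose instead that an untested abstainer is not counted as missing, because the survey was answered. That person still lacks a negative CO test, and the complete-case rate becomes A·r·c / 106.8: 6.6% at 50% return and 10.5% at 80%. Both readings fall short of 13.1%.

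**Step 3. Who is dropped.** At 70% return, complete case drops 13.2 survey non-responders and 15.6 × 0.3 = 4.7 untested abstainers per arm. The untested abstainers are 4.7 / 17.9 = 26% of those dropped (7% to 46% over quit rates of 8% to 19% and return of 50% to 90%).

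**Step 4. Comparison of arms (c = 100%).** Same formulas, applied to each arm.

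| Self-report, % | Kit return, % | Missing = non-abstinent, % | OR | Complete case, % | OR |
|---|---|---|---|---|---|
| 13 vs 13 | 80 vs 60 | 10.4 vs 7.8 | 1.37 | 12.0 vs 9.3 | 1.33 |
| 13 vs 13 | 70 vs 70 | 9.1 vs 9.1 | 1.00 | 10.7 vs 10.7 | 1.00 |
| 13 vs 8 | 100 vs 100 | 13.0 vs 8.0 | 1.72 | 14.6 vs 9.0 | 1.73 |
| 13 vs 8 | 70 vs 70 | 9.1 vs 5.6 | 1.69 | 10.7 vs 6.5 | 1.73 |
| 13 vs 8 | 50 vs 80 | 6.5 vs 6.4 | 1.02 | 7.9 vs 7.3 | 1.08 |

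Unequal return can create a difference (first row) or hide one (last row), and complete case barely corrects either. Equal 70% return leaves the odds ratio almost unchanged but shrinks the absolute difference from 5.0 to 3.5 points.

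**The case against.** The strongest reply has four parts.

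- **Definition.** Someone without a negative CO test is unconfirmed by the meaning of the endpoint. A reader might infer that the plan relabels untested abstainers as smokers. The documents do not say so: these people have self-reported smoking data, still count as abstinent on the self-report endpoint, and both results are always shown. This stands against that inference. It does not rescue the complete-case analysis, which is too low on either reading.
- **Planned imputation.** Multiple imputation is announced in the same sentence as complete case, so a better method is already promised. This stands in part. Imputation helps only if it covers the test result given self-report. A model that ignored self-report would give untested abstainers something close to the complete-case rate.
- **No evidence of unequal return.** A reader might infer that kit return will differ by arm because app acceptability is the primary question. The documents state no such expectation. In the earlier trial against the same control app, engagement differed strongly (p < .0001) but survey retention did not differ between arms (Section 2.2.3), and testing is paid for (Section 7.5). Survey retention is not kit return, but it is the nearest evidence. Bias between arms is therefore conditional.
- **Size.** With 13% in both arms, a 90% pass rate and 60% vs 40% return, the confirmed rates are 7.0% vs 4.7%, or 8.4 vs 5.6 people. That is 2.3 points against a standard error of about 3.0, on a secondary endpoint of a pilot that is not powered for arm differences (Section 14.3). This stands, and it keeps the point minor.

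**Conclusion.** The point holds for the secondary biochemically confirmed endpoints and is minor. The firm part is the level of the complete-case rate. Because only self-reported abstainers are tested, that rate is too low whenever some kits are not returned, even at random: 7.1% at 50% return and 10.8% at 80%, against 13.1%. These sizes rest on assumed values of 13% self-reported abstinence and a 90% pass rate, and on the plan's 89% survey response; the direction does not depend on them.

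Any effect on the arm comparison is conditional on unequal kit return, for which the documents give no figure. With equal return only the absolute difference suffers.

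It would also be wrong to conclude that complete case drops nobody but abstainers. It drops about 13 survey non-responders per arm as well; the statement is true only among survey responders. The self-reported cessation endpoint and the acceptability outcomes are unaffected.

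**What to change.** In Section 14.2 and Appendix A, Section 7.2, for the confirmed endpoints:

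1. Keep missing = non-abstinent as the main, conservative analysis, and state that a self-reported abstainer without a test result counts as not confirmed.
2. Replace the complete-case analysis with the multiple imputation already planned, specified so that the missing test result is imputed only among self-reported abstainers. Say separately how survey non-responders are handled.
3. Report by arm, at 8 weeks and 6 months, the numbers asked to test, returned and passed.

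The cost is some wording, one table and a few lines of analysis; no new data are needed. The downside is that the imputation assumes that untested abstainers pass as often as tested ones, which is what verification is meant to question. It would also rest on few kits: at 40% to 70% return, 15.6 abstainers yield about 6 to 11 per arm. Pooling the pass rate over arms would bring the arm ratio back to the self-reported one. It should therefore be a sensitivity analysis only.
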